### 5.2 Derivations and Definitions

- For final analysis all time points, including Visit 1 (Day 0), Visit 2 (Day 28) and Visit 3 (Day 56) will be analyzed.
- Seroconversion rate for anti-zika-rsp VNT titers is defined as proportion of subjects achieving anti-zika-rsp VNT titers  $\geq 20$  at a certain time point.

- Seroconversion rate for anti-zika-rsp ELISA titers is defined as 4-fold increase over baseline (Visit 1 –Day 0). If no Visit 1 (Day 0) sample is available, no seroconversion will be determined.
- For MV ELISA, Zika ELISA, NT and T-Cell an analysis of positive versus negative values is planned. Since such a definition could not be discussed and communicated with the central laboratory at the time of generation of this SAP, details about used limits will be shown as footnotes in the corresponding tables and explained in the Clinical Study Report.
- For the different immunogenicity parameter there are different lower limit of quantification (LLOQ). [redacted]
  - In data listings, the original reported value “<LLOQ” will be displayed.
  - For calculations (GMT, median...) the half of the true LLOQ value will be used for such values.
  - If another unexpected value is reported as LLOQ in the data than mentioned here, the half value of the reported LLOQ will be used for the calculations.
- For the different immunogenicity parameters there are different upper limits of quantification (ULOQ) [redacted]
  - In data listings, the original reported value “>ULOQ” will be displayed.
  - For calculations (GMT, median...) the ULOQ value will be used for such values.
  - If another unexpected value is reported as ULOQ in the data than mentioned here, this ULOQ value will be used for calculations.
- For analysis using interval-censored data an interval will be defined for every observation. Observations between LLOQ and ULOQ will be handled as interval with left limit and right limit being the observed value. For values <LLOQ the interval will be left-censored with the LLOQ as right limit. For values >ULOQ the interval will be right-censored with the ULOQ as left limit.

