The current Zika epidemic is the largest epidemic ever recorded for this virus. Usually, a Zika infection is mild with symptoms such as fever, rash, conjunctivitis and joint pain lasting for several days to a week. People often do not realize they have been infected. Symptoms of Zika are often like other viruses spread through mosquito bites, like dengue and chikungunya. Although infection with Zika virus was usually associated to mild disease, its emergence in the Americas has coincided with a steep increase in patients developing Guillain-Barré syndrome. Moreover, infection with Zika virus has been linked to the birth of babies with neurological complications, in particular congenital microcephaly (WHO, 2016; ECDC 2015; Soares de Araújo, 2016), and it was shown that when pregnant women are exposed to Zika virus during the first trimester of pregnancy, the risk of microcephaly for the newborn is increased 50 times from 2/10 000 to 1/100 (Cauchemez, 2016). In Feb 2016, the WHO declared the suspected link between Zika virus and neurological disorders and neonatal malformations a Public Health Emergency of International Concern.

In this context, in March 2016, experts gathered at WHO agreed that the development of a preventive vaccine is a major priority to respond to Zika epidemics in the future (WHO, Media centre, 2016). A clear target product profile (TPP) for this vaccine is still under work, but pragmatic strategies were asked to fast track the development of a safe and effective product. Due to the established link between Zika virus infection and the appearance of congenital microcephaly in babies born to infected mothers, one could argue that a Zika vaccine has to be suitable for use in pregnant women. However, no licensed vaccine is currently recommended for the use in pregnant women. Moreover, with the demonstrated association of Zika infection with Guillain-Barré syndrome, the observation of possible sexual transmission,

and the appearance of developmental defects probably appearing very early in pregnancy, it is very likely that the TPP will be addressed to the general population. In any case a Zika vaccine will have to demonstrate an excellent safety profile, particularly concerning the risk of neurotropism.

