### 7.3 Exclusion Criteria

The subject may not be enrolled in the study if any of the following applies:

1. Participation in another clinical study (including exposure to an investigational medicinal product or device) within one month before the screening visit or planned concurrent participation in another clinical study before completion of the treatment period (day 56)
2. History of immunodeficiency, known human immunodeficiency virus (HIV) infection or current hepatitis B/C infection
3. Strong anamnestic evidence for or confirmed history of or current infection with Zika- or Dengue-virus
4. History of drug addiction including alcohol dependence within the last 2 years

5. Inability or unwillingness to avoid intake of more than around 20g alcohol per day during 48 hours after each vaccination (equals roughly 0.5 L beer or 0.25 L of wine)
6. Vaccination within 4 weeks prior to first vaccination or planning to receive any non-study vaccine until end of treatment period (day 56)
7. Prior receipt of any Zika or Chikungunya vaccine
8. History of moderate or severe arthritis or arthralgia within the past 3 months prior to Screening Visit
9. Recent infection within 1 week prior to Screening Visit (possibility of deferral)
10. Blood donations including plasma donations, 90 days prior to Screening Visit and anticipated blood, plasma, tissue, sperm, or organ donation, throughout the study until end of treatment period (day 56)
11. Clinically relevant history of renal, hepatic, gastrointestinal, cardiovascular, respiratory, skin, haematological, endocrine, inflammatory, autoimmune, or neurological diseases or clinically relevant abnormal laboratory values, that in the opinion of the investigator may interfere with the aim of the study
12. History of neoplastic disease (excluding non-melanoma skin cancer that was successfully treated) within the past 5 years or a history of any haematological malignancy
13. Behavioural, cognitive, or psychiatric condition that in the opinion of the investigator affects the ability of the participant to understand and cooperate with the study protocol
14. History of severe adverse reactions to vaccine administration, including anaphylaxis and related symptoms, such as urticaria, respiratory difficulty, angioedema and abdominal pain to vaccines, or history of allergic reaction likely to be exacerbated by any component of the vaccine

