### 12.2 Methods of Statistical Immunogenicity Analysis

The immunogenicity analysis will compare the anti-zika-rsp VNT antibody geometric mean titre (GMT) in the Per Protocol (PP) analysis population between the treatment groups. GMTs and GMT ratios will be estimated by applying an analysis of variance including the factor treatment group. This will be done using  $\log_{10}$  transformed data and taking the anti-log of the resulting point estimates for the least squares means, least squares means differences and the corresponding 2-sided 95% CIs.

P-values will also be provided to compare GMTs between the treatment groups adjusted for multiple comparisons according to Tukey-Kramer. Seroconversion rates will be compared between groups using Fisher's exact test.

Seroconversion will be defined as anti-zika-rsp VNT titres  $\geq 20$ .

ZIKA-RSP- and measles- ELISA titres will be analysed as described above.

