| Version 2.1 (28 Sep 2020) |  |   |
| 1.                        | PRNT 50 was replaced with VNT.  | A Plaque Reduction Neutralization Test method was replaced with another, highly similar serum sample test termed Virus Neutralization Test.   |
| 4.5                       |  |   |
| 5.2                       |  |   |
| 6.1                       |  |   |
| 6.2.2                     |  |   |
| 6.5                       |  |   |
| 8.5.1                     |  |   |
| 8.5.3                     |  |   |
| 8.5.4                     |  |   |
| 8.11.2                    | Description of usage of a Plaque reduction neutralization assay was replaced with description of usage of a Virus Neutralization Test. |   |
| 8.11.4                    | PRNT 50 was replaced with VNT.  |   |
| 12.2                      |  |   |
| 12.2                      | Seroconversion will be defined as anti-zika-rsp VNT titres $\geq 20$ 10.   | Neutralizing antibodies were quantified with a slightly different assay than originally planned. This VNT has a Lower Limit of Quantification (LLOQ) of 20, requiring us to adapt the protocol to accommodate the more stringent cut-off. |

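### VNT seroconversion is defined as a titre of 20 or more at a visit, without reference to Day 0, so the planned rate measures seropositivity rather than conversion.

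*Combined protocol and SAP*

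**What the plan says.** Protocol 12.2: "Seroconversion will be defined as anti-zika-rsp VNT titres" of at least 20. SAP 5.2: "Seroconversion rate for anti-zika-rsp VNT titers is defined as proportion of subjects achieving anti-zika-rsp VNT titers" of at least 20 at a given time point. Neither sentence requires a negative Day 0 sample or a rise from Day 0, and no other section adds such a condition.

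The next bullet of SAP 5.2 treats the other Zika assay differently: "Seroconversion rate for anti-zika-rsp ELISA titers is defined as 4-fold increase over baseline" (Visit 1, Day 0). It adds: "If no Visit 1 (Day 0) sample is available, no seroconversion will be determined". There is no matching sentence for VNT.

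On timing, SAP 5.2 says: "For final analysis all time points, including Visit 1 (Day 0), Visit 2 (Day 28) and Visit 3 (Day 56) will be analyzed". SAP 7.1 lists the VNT seroconversion rate as a by-visit table (2.3.1.4), and SAP 2.6 compares seroconversion and positivity rates between groups by the Fisher-Freeman-Halton test, with no baseline term.

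On the cut-off, the protocol's revision index states: "This VNT has a Lower Limit of Quantification (LLOQ) of 20". The seroconversion threshold is therefore the assay's quantification limit.

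On baseline status, exclusion criterion 3 (protocol 7.3) covers "Strong anamnestic evidence for or confirmed history of or current infection with Zika- or Dengue-virus", and criterion 7 excludes earlier receipt of a Zika vaccine. Screening virology (protocol 8.11.1) consists of hepatitis B, hepatitis C and HIV. The first Zika antibody sample is taken at Visit 1, on the day of randomisation.

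**The concern.** Seroconversion means a change from negative to positive, or a defined rise. The VNT rule contains no change. A participant at or above 20 on Day 0 whose titre never moves is counted as converted on Days 28 and 56. Taken with the by-visit table and the list of time points, the rule also yields a seroconversion rate before anyone has been vaccinated.

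Nothing in the design ensures that everyone starts below 20. Entry relies on history or a confirmed diagnosis, and protocol 4.2 says of Zika: "People often do not realize they have been infected". With groups of 8 to 14, a single such participant is visible in the rate and can move an exact p-value a long way.

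At stake is the meaning of one secondary immunogenicity result. The optimal-dose objective draws on VNT immunogenicity, and a reader comparing VNT with ELISA seroconversion in the same report would be comparing two different quantities.

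**Working it through.** **No plan figure to reproduce.** Neither document gives a power calculation, an expected seroconversion rate or a Day 0 positivity rate. Group sizes are 14 + 14 + 12 + 8 = 48 (protocol 6.3).

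**1. The two rules side by side (SAP 5.2)**

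| | VNT | Zika ELISA |
|---|---|---|
| Criterion | titre ≥ 20 at the visit | 4-fold rise over Day 0 |
| Uses Day 0 | no | yes |
| Day 0 sample missing | no rule | not determined |
| ≥ 20 at Day 0, unchanged later | converted | not applicable |
| Unchanged from Day 0 | converted if ≥ 20 | not converted |

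**2. Effect of one Day 0 positive.** Counting one such participant as converted rather than not converted, in the same denominator, changes the rate by 1/n:
- A or B: 1/14 = 7.1 points
- C: 1/12 = 8.3 points
- D: 1/8 = 12.5 points

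**3. How many to expect.** Let b be the assumed proportion at 20 or above on Day 0. The expected number is 48b and the chance of at least one is 1 − (1 − b)^48.

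| b (assumed) | Expected of 48 | P(at least one) |
|---|---|---|
| 0 | 0 | 0 |
| 2% | 0.96 | 0.62 |
| 5% | 2.4 | 0.91 |
| 10% | 4.8 | 0.99 |

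**4. Direction of the error.** Let s be the true conversion rate among vaccinated Day 0 negatives. Assume that Day 0 positives stay at 20 or above and that no placebo Day 0 negative converts. As defined, the expected rate is b + (1 − b)s on vaccine and b on placebo, a difference of (1 − b)s. Among Day 0 negatives alone it is s against 0. With s = 50% (assumed), the difference falls from 50 points to 47.5 at b = 5% and 45 at b = 10%. Rates rise in both arms and the contrast shrinks.

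**5. Sensitivity of the tests, with hypothetical counts**
- Two groups, Fisher's exact test: 7/14 against 0/8 gives p = 0.022; 7/14 against 1/8 gives p = 0.167.
- Four groups, Fisher-Freeman-Halton: 8/14, 4/14, 4/12, 0/8 gives p = 0.052; with 1/8 on placebo, p = 0.19.

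**6. Does a Day 0 condition add power?** Fisher's exact test, A against D, two-sided 0.05 (a level assumed here), s = 50%:

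| b | As defined | Day 0 positives kept, none rising | Day 0 positives excluded |
|---|---|---|---|
| 5% | 0.53 | 0.53 | 0.61 |
| 10% | 0.46 | 0.45 | 0.57 |
| 20% | 0.34 | 0.31 | 0.47 |

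Keeping them in the denominator gives essentially no gain. Excluding them helps at s = 50%, but not at s = 30% (at b = 10%, 0.113 as defined against 0.103). Power is therefore not the argument for the change.

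**The case against.** The wording of the rule is not in dispute; its consequence is. Five points can be made against the concern.

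- **Seroconversion is not the main VNT comparison.** A reader might infer that it is. The documents do not support that: protocol 12.2 and SAP 2.6 open with the GMT, and the ANOVA, the Tukey-Kramer adjustment and the censoring sensitivity analysis all concern GMTs. The primary endpoint is the adverse event rate. This stands.
- **Day 0 positivity may be nil.** Known Zika or Dengue infection and earlier Zika vaccination are excluded, and the single site is in Vienna. The protocol's remark on unnoticed infection describes the epidemic, not these volunteers. This stands as a limit on size, but the entry criteria do not guarantee a negative Day 0 titre.
- **The rule does not favour the vaccine.** A reader might infer an inflated vaccine effect. Under randomisation, Day 0 positives fall in every arm and on average dilute the contrast; only chance imbalance could work the other way. This stands.
- **The predecessor trial is no evidence.** Protocol 4.4.1 reports one seroconversion after placebo. It concerned a different vaccine, the definition used is not given, and nothing says that participant was positive at baseline. It should carry no weight here.
- **The data remain visible.** Titres are tabulated by visit including Day 0, and Listing 2.3.1 shows each participant's titre and seroconversion status. A reader could pick out Day 0 positives, but the planned rate and its test would still be uncorrected.

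**Conclusion.** The rule is wrong as written and should be changed, though the fault is confined to one of two planned VNT comparisons in a phase I safety trial. What protocol 12.2 and SAP 5.2 call VNT seroconversion is the proportion with a quantifiable titre at a visit.

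The effect starts at zero and rises with Day 0 positivity, which the documents do not state. The 2–10% range, the values of s and the assumption that Day 0 positives remain at 20 or above are illustrations, not findings. The effect per participant follows directly from the group sizes.

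The benefit of the change is a rate that measures what its name says and can be read beside the ELISA rate. It should not be presented as a gain in power or as the removal of a bias towards the vaccine.

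**What to change.** In protocol 12.2 and SAP 5.2:

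1. Define VNT seroconversion at Visits 2 and 3 only, as a Day 0 titre below 20 and a titre of 20 or more at the visit.
2. State how participants at 20 or above on Day 0 are handled: either leave them out of the denominator, or count them only on a pre-stated fold rise, for example the 4-fold rise already used for ELISA. The choice belongs to the sponsor but must be written down.
3. Treat VNT seroconversion as not evaluable without a Day 0 sample, as for ELISA.
4. Do not replace the rule with a 4-fold rise for everyone without saying so. With values below the LLOQ set to half of 20, that is 10, a 4-fold rise requires 40, which is stricter than 20.
5. Keep the present measure, by visit and including Day 0, as the proportion with a titre of 20 or more (seropositivity). State that cut-off, because SAP 5.2 leaves the NT positivity limit undefined.

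The cost is a few sentences and one revised table; Day 0 VNT samples are already collected. Timing needs care. SAP 2.4 unblinds sponsor and analysis staff at the Day 56 preliminary analysis, while SAP 2.1 defers immunogenicity to the final analysis. The documents do not show whether VNT results have been seen by treatment group. If they have, document the change as an amendment (protocol 16.1) and report both rates.

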## 6. SAFETY ANALYSIS

All safety analyses will be performed for the safety population.

### 6.1 Extent of Exposure

#### 6.1.1 Data points

The following information will be analyzed descriptively and corresponding details on the subject level will be provided in data listings:

- Treatment duration
- Study duration
- Study vaccine administration (will be listed only)

For details on table and listing content, see Section 7.

### 6.1.2 *Derivations and Definitions*

- Treatment duration [days] = date of last administered vaccine – date of first vaccination +1 (only if more than one vaccine administered)
- Study duration [days] = date of last attended visit (or date of study discontinuation, if applicable) – date of signed informed consent + 1

## 6.2 Adverse Events

### 6.2.1 *Data points*

The following analyses will be provided for all Adverse Events:

- Adverse event overview for solicited and unsolicited events (e.g. any AE, any SAE, any related AE).
- Solicited Adverse Events by symptom
- Solicited Adverse Events by symptom and severity
- Unsolicited Adverse Events by SOC and PT, overall and for specific types of Adverse Events (e.g. SAEs, related AEs)
- Unsolicited Adverse Events by severity and for specific types of Adverse Events
- Unsolicited Adverse Events by causality and for specific types of Adverse Events

For details on table and listing content, see Section 7.

### 6.2.2 *Derivations and Definitions*

- All solicited and unsolicited Adverse Events up to Day 56 (Visit 3) will be analyzed for the preliminary analysis and all AE in the database for the Final Analysis. The following rules will be applied to identify AEs up to Day 56 for preliminary analysis: In general, all AE with start date prior to or at Visit 3 are considered. If a subject has no Day 56 visit (Visit 3) then all AEs within 56 days from Visit 1 (Day 0) (Visit 1 + 56 days) are included. If start date of AE is incomplete (e.g. missing start day) and the AE could theoretically be within Visit 3, or if Visit 3 is not available, within 56 days from Visit 1 (Visit 1 + 56 days), it will be handled as AE up to Day 56 (Visit 3) and thus be included in the preliminary analysis. If start date of AE is unknown it will be handled as AE up to Day 56 visit (Visit 3) and thus be included in the preliminary analysis.
- Percentages for AE rates are based on N (treatment group totals).
- An Adverse Events is considered to be related to study treatment if “Relationship to Study Treatment” is answered with “definitely”, “probably” or “possibly” or the causality is missing.
- Tables showing “severe” events will include events with grade 3 or 4 or missing grade.
- In tables showing subjects with AEs by maximum severity, subjects will be counted only in the highest grading category (=“potentially life threatening”), but events will be counted in each reported grading category.

Adapted from:

STAT03\_A Statistical Analysis Plan

Version 6.0, Effective Date 16-Feb-2018

Confidential and intellectual property of Assign DMB. No part of this document or its contents may be duplicated, referenced, published or otherwise disclosed in any form or by any means without prior written consent of Assign DMB.

- In tables showing AEs by causality, subjects will be counted only in the strongest relationship category ("definitely"), but events will be counted in each category.

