#### 6.2.2 Secondary Endpoints

- Rate of solicited and unsolicited AEs, as well as, reported serious adverse events (SAEs) up to study day 182 (long-term safety) compared between the 4 different treatment groups.
- Immunogenicity on study days up to study day 56 as confirmed by the presence of functional anti-zika antibodies as determined by VNT and by ELISA

- Cell-mediated immunity specific for ZIKA-RSP, up to study day 56, confirmed by the presence of specific functional CD4+ and CD8+ T-cells
- Safety laboratory parameters (haematology, serum chemistry, urinalysis)

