### 11.5 Post Vaccination Reactogenicity Assessments

All participants enrolled in the study and who receive at least one study treatment (MV-ZIKA-RSP or placebo) will be followed up 28 days after each study treatment. Solicited and unsolicited AEs will be recorded at each visit until the end of the study at Visit 4.

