## 11.7 Subject Diary

The participants will be instructed to complete a diary for 7 days after each vaccination to document local and systemic tolerability as well as body temperature.

Solicited local and solicited systemic AEs will be assessed by the participants themselves by checking for presence of the listed symptoms and measuring the size of the affected area where appropriate (a template will be provided for local reaction grading, as shown in Appendix 1). The diary will also provide space for recording unsolicited AEs and concomitant medication.

Recording should be done approximately at the same time each day, starting on the day of vaccination. The first entry should be made 6 hours  $\pm 1$ h after vaccination at Visit 1 and Visit 2.

The participants' diaries will be collected and verified for completeness by the investigator at Visit 2 and Visit 3. Any AE recorded in the subject diaries will be entered in the eCRF by the investigator or authorised delegates. The investigator will re-evaluate the severity of the reported local and systemic AEs according to the below Tables 5 and 6.

Diary solicited systemic AEs include nausea, vomiting, headache, and fatigue, also to be documented in the eCRF.

In addition, body temperature will be recorded daily for 7 days and fever will be graded by the investigator according to the FDA Guidance for Industry. For details see below Table 6. Table 5. Grading of local reactions

| Local reaction to injectable product | Mild (grade 1) | Moderate (grade 2) | Severe (grade 3) | Potentially life threatening (grade 4) |
|--------------------------------------|----------------|--------------------|------------------|--|
|--------------------------------------|----------------|--------------------|------------------|--|

|   |   |  |  |  |
|---|---|--|--|--|
| Pain                             | Does not interfere with activity            | Interfere with activity or repeated use of non-narcotic pain reliever  | Prevents daily activity or repeated use of non-narcotic pain reliever                    | Emergency room (ER) visit or hospitalisation |
| Tenderness                       | Mild pain to touch                          | Pain with movement   | Significant pain at rest   | ER visit or hospitalisation                  |
| Erythema/ Redness    | ≤ 5 cm                                      | 5.1–10 cm  | > 10 cm  | Necrosis or exfoliate dermatitis             |

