### 12.3 Methods of Statistical Safety Analysis

The analysis of safety will be performed in the Safety Population.

AEs and concomitant diseases will be coded using the MedDRA coding dictionary.

Solicited AEs (reactogenicity):

Solicited local and systemic AEs gathered by the participants' diaries will be summarised for the 7-day period, by AE grading (mild, moderate, severe) and by treatment group. The number and percentage of participants with AEs will be presented. Fisher exact tests will be provided for a comparison of AE rates between treatment groups in summary tables.

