#### 1.1.2 Secondary Objectives

- To investigate long-term safety, up to study day 182, after first immunization

Long term safety and tolerability will be assessed by means of a phone call where participants will be asked about any adverse event (solicited, unsolicited or serious adverse event) experimented after the Visit 3 (day 56)

- To investigate immunogenicity up to day 56 after first immunization consisting in one or two vaccinations with different doses

To cover this objective the presence of functional anti-zika antibodies will be determined by means VNT and ELISA at the following time points: Visit 1 (day 0), Visit 2 (day 28) and Visit 3 (day 56) after first vaccination

- To get information about the optimal dose of MV-ZIKA-RSP vaccine regarding safety, tolerability and immunogenicity

An evaluation of the optimal dose will be determined after analysis of the safety, tolerability and immunogenicity (VNT)

- To investigate specific cell mediated immunity induced by all different treatment groups

Cell mediated immunity up to day 56 will be assessed by T cell analysis of PBMC isolated on study days 0, 28 and 56

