## 2.14 Changes in the Conduct of the Study or Planned Analysis

No changes to the statistical analysis as compared to CSP are planned.

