| 1.4.1.18   | 2.4.1.18 | Subjects with medically attended unsolicited Adverse Events by SOC and PT (Safety Population)                   |  |
| 1.4.1.19   | 2.4.1.19 | Subjects with related severe unsolicited Adverse Events by SOC and PT (Safety Population)                       |  |
| 1.4.1.20   | 2.4.1.20 | Subjects with related serious unsolicited Adverse Events by SOC and PT (Safety Population)                      |  |
| 1.4.1.21   | 2.4.1.21 | Subjects with related medically attended unsolicited Adverse Events by SOC and PT (Safety Population)           |  |
| 1.4.1.22   | 2.4.1.22 | Subjects with unsolicited Adverse Events leading to second Vaccination not administered (Safety Population)     |  |
| 1.4.1.23   | 2.4.1.23 | Subjects with unsolicited Adverse Events caused study discontinuation (Safety Population)                       |  |
| 1.4.1.24   | 2.4.1.24 | Subjects with at least one unsolicited Adverse Event by Maximum Severity (Safety Population)                    |  |
| 1.4.1.25   | 2.4.1.25 | Subjects with at least one medically attended unsolicited Adverse Event by Maximum Severity (Safety Population) |  |
| 1.4.1.26   | 2.4.1.26 | Subjects with at least one unsolicited Adverse Event by Causality (Safety Population)                           |  |
| 1.4.1.27   | 2.4.1.27 | Subjects with at least one medically attended unsolicited Adverse Event by Causality (Safety Population)        |  |
| 1.4.1.28   | 2.4.1.28 | Subjects with at least one serious unsolicited Adverse Event by Causality (Safety Population)                   |  |
| NOTE: Adverse Event tables will also be provided for final analysis but including all AEs reported during the study. For the preliminary analysis the wording "up to Day 56" and for the final analysis "up to study end" will be added in the title of AE Table x.4.1.2-x.4.1.28. |          |   |  |
| Laboratory Parameters   |          |   |  |
| 1.4.1.29   | n/a      | Absolute Values for Hematology Parameters by Parameter and Visit (Safety Population)                            |  |
| 1.4.1.30   | n/a      | Absolute Values for Clinical Chemistry Parameters by Parameter and Visit (Safety Population)                    |  |

|                                |     |   |  |
|--------------------------------|-----|---|--|
| 1.4.1.31                       | n/a | Absolute Values for Coagulation Parameters by Parameter and Visit (Safety Population)                       |  |

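### The documents disagree on the time window for solicited adverse events; the SAP takes only the long windows, drops the protocol's 7-day summary and gives no onset rule, so late systemic symptoms can be counted as reactogenicity

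*Combined protocol and SAP*

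**What the plan says.** **Short window (protocol).** Section 12.3, under its reactogenicity heading, takes solicited events from the diaries; they "will be summarised for the 7-day period, by AE grading (mild, moderate, severe) and by treatment group". Section 11.7 matches this: "The participants will be instructed to complete a diary for 7 days after each vaccination to document local and systemic tolerability". Section 10.2 also ties the diary to 7 days after each vaccination.

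**Long windows (protocol).** The synopsis has solicited events summarised by severity and term to Day 56 in the preliminary analysis. The secondary endpoint in 6.2.2 is "Rate of solicited and unsolicited AEs, as well as, reported serious adverse events (SAEs) up to study day 182 (long-term safety"), compared between the four groups. Section 11.5 states: "Solicited and unsolicited AEs will be recorded at each visit until the end of the study at Visit 4". Section 5.2, repeated in SAP 1.1.2, describes the Day 182 call, in which "participants will be asked about any adverse event (solicited, unsolicited or serious adverse event) experimented after the Visit 3 (day 56").

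**SAP.** Section 6.2.2: "All solicited and unsolicited Adverse Events up to Day 56 (Visit 3) will be analyzed for the preliminary analysis", and all events in the database for the final analysis. The note in 7.1 adds: "Adverse Event tables will also be provided for final analysis but including all AEs reported during the study". It labels every table from x.4.1.2 to x.4.1.28 with Day 56 or study end, which includes all the solicited tables (x.4.1.3 to x.4.1.5 and x.4.1.8 to x.4.1.12). No 7-day table is listed. Section 2.6 applies the Fisher-Freeman-Halton test across groups to all adverse event tables. Section 2.8 mentions a solicited/unsolicited assignment for each event but gives no rule for making it. Section 2.14: "No changes to the statistical analysis as compared to CSP are planned".

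**The concern.** A reactogenicity table is read as what happened in the days after injection. That reading needs a fixed window tied to each dose. Here the window is 7 days per injection in one place, Day 56 in another and Day 182 in others, and the SAP carries forward only the last two.

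The listed systemic symptoms, such as headache, fatigue and nausea, also occur without vaccination. If those starting after the diary closes are typed as solicited, they enter every group's rate, raise the placebo rate most and shrink the visible difference. Tolerability of one or two vaccinations is part of the primary objective, and with groups of 14, 14, 12 and 8 there is little signal to spare. The SAP's statement of no change also tells a reader that the 12.3 summary will be delivered, when no listed table delivers it.

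**Working it through.** **1. Can an event called solicited start after the diary?** The second injection is on Day 28 ± 3 and the diary runs 7 days, so the last diary closes by about Day 28 + 3 + 7 = 38. The Day 182 call asks about solicited events after Visit 3, which is Day 56 ± 3, so Day 53 at the earliest. Any solicited event from that call starts at least about 53 − 38 = 15 days after the last diary closed. The text therefore allows late solicited events, although it does not define them.

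**2. How much longer are the SAP windows?** Diary time is 2 × 7 = 14 days. The SAP windows are 56/14 = 4 times and 182/14 = 13 times as long.

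**3. What could dilution look like?** The documents give no background rate, effect size or alpha for solicited events, so there is no figure of the plan to reproduce and every rate below is assumed.

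- b: background probability of a listed systemic symptom over 14 days (10%, 25% or 40%), at a constant hazard
- e: vaccine effect, arising only inside the diary windows and equal in Groups A, B and C (30% or 50%)
- f: share of later background symptoms that end up typed as solicited (0, 0.25 or 1)
- W: table window (56 or 182 days)

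Effective exposure E = 14 + f(W − 14). Placebo rate = 1 − (1 − b)^(E/14). Vaccine rate = 1 − (1 − e)(1 − b)^(E/14). Difference = e(1 − b)^(E/14).

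Worked case, b = 25% and e = 50%:

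- Diary windows: E = 14. Placebo 25%, vaccine 1 − 0.5 × 0.75 = 62.5%, difference 37.5 points.
- Day 56, f = 0.25: E = 14 + 0.25 × 42 = 24.5. Placebo 40%, vaccine 70%, difference 0.5 × 0.75^1.75 = 30 points.
- Day 56, f = 1: E = 56. Placebo 68%, vaccine 84%, difference 0.5 × 0.75^4 = 16 points.
- Day 182, f = 0.25: E = 14 + 0.25 × 168 = 56, the same as the line above.
- Day 182, f = 1: E = 182. Placebo 98%, vaccine 99%, difference 0.5 × 0.75^13 = 1 point.

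Difference in percentage points over the assumed range:

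| e | b | Diary only (or f = 0) | Day 56, f = 0.25 | Day 56, f = 1, or Day 182, f = 0.25 | Day 182, f = 1 |
|---|---|---|---|---|---|
| 50% | 10% | 45.0 | 41.6 | 32.8 | 12.7 |
| 50% | 25% | 37.5 | 30.2 | 15.8 | 1.2 |
| 50% | 40% | 30.0 | 20.5 | 6.5 | under 0.1 |
| 30% | 10% | 27.0 | 24.9 | 19.7 | 7.6 |
| 30% | 25% | 22.5 | 18.1 | 9.5 | 0.7 |
| 30% | 40% | 18.0 | 12.3 | 3.9 | under 0.1 |

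For b = 25% and e = 50%, exact power of the Fisher-Freeman-Halton test (14/14/12/8, assumed alpha 0.05) is 33%, 24%, 14% and 1% across the last four columns. Power is low even in the diary windows, so the effect on the descriptive rates matters more than the p-value.

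At f = 0 the Day 56 and study-end tables hold the same events as a 7-day table, and nothing changes.

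**The case against.** A reader might infer that the SAP replaced a clear 7-day protocol window with longer ones, and that the reactogenicity rates are therefore diluted. Neither half is supported.

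- **The protocol also sets the longer windows.** SAP 6.2.2 follows the synopsis closely to Day 56 and the secondary endpoint to Day 182. The conflict begins in the protocol and the SAP inherits it. SAP 2.14 is inaccurate only in that the 12.3 summary has been dropped.
- **Structured collection stays at 7 days per dose.** Visits and calls rely on general questions (protocol 10.2), so later ascertainment is weaker and of a different kind.
- **Dilution needs later symptoms to be typed as solicited.** Section 12.3 describes solicited events as coming from the diaries, and 11.7 gives the diary a separate space for unsolicited ones. If coding follows the diary, there is no dilution.
- **There is no sound anchor for size.** The predecessor trial's 62.5% placebo headache is 5 of 8 participants, for a different candidate, with no stated window. Solicited events there were more frequent on placebo (100%) than on vaccine (70%).
- **Partial recovery is possible.** The solicited summary tables have rows for related events, and the listings give start times.

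All five points stand. They limit the claim but do not remove it: sections 5.2 and 11.5 of the protocol point the other way on coding, so the classification is undefined, and no listed table supplies the 7-day summary.

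**Conclusion.** The point holds as a conflict over the window together with a missing onset rule. As written, the plan can count listed systemic symptoms that start after the diary closes as reactogenicity, and it omits the summary promised in protocol 12.3 without declaring this.

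The resulting dilution is possible but not established. Its size depends on the share of late symptoms typed as solicited and on background and vaccine rates that the documents do not give; the figures above are illustrations, running from no change to near-complete loss of the difference. Exposure is mainly in systemic symptoms; injection-site reactions should gain little background. The primary endpoint, all adverse events to Day 56, does not depend on the solicited label and is unchanged. The rule should be corrected because tolerability is a stated objective and the remedy is cheap.

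**What to change.** In SAP 6.2.2, define solicited adverse events for analysis as listed symptoms with onset within the 7-day diary period after each injection. Classify the same symptoms with later onset as unsolicited, so that they still count in the all-event tables to Day 56 and Day 182. Title tables x.4.1.3 to x.4.1.5 and x.4.1.8 to x.4.1.12 as covering 7 days after vaccination, and exempt them from the titling note in 7.1.

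Reconcile with this rule:

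- protocol: the synopsis (statistical methods and secondary endpoints), 5.2, 6.2.2, 11.5 and 12.3
- SAP: 1.1.2, 1.3.2 and 2.14

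Cost: one derivation from onset and injection dates already collected, retitled tables, and wording edits that include the Day 182 secondary endpoint. The protocol edits need a written amendment under protocol 16.1. No new data are required. If every solicited record already falls inside the diary windows, the counts stay the same and the tables become interpretable.
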